7.2. Participant Discontinuation/Withdrawal From the Study

A participant may withdraw from the study at any time at their own request. Reasons for discontinuation from the study include the following:

- Refused further follow-up;
- Lost to follow-up;
- Death;
- Study terminated by sponsor.

At the time of discontinuing from the study, if possible, an discontinuation visit should be conducted. See the [SoA](#) for assessments to be collected at the time of study discontinuation and follow-up and for any further evaluations that need to be completed.

The discontinuation visit applies only to participants who are enrolled/randomized and then are prematurely withdrawn from the study. Participants should be questioned regarding their reason for withdrawal.

If a participant withdraws from the study, they may request destruction of any remaining samples taken and not tested, and the investigator must document any such requests in the site study records and notify the sponsor accordingly.

If the participant withdraws from the study and also withdraws consent (see [Section 7.2.1](#)) for disclosure of future information, no further evaluations will be performed and no additional data will be collected. The sponsor may retain and continue to use any data collected before such withdrawal of consent.

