7.3. Lost to Follow-Up

A participant will be considered lost to follow-up if the participant repeatedly fails to return for scheduled visits and is unable to be contacted by the study site.

The following actions must be taken if a participant fails to return to the clinic for a required study visit:

- The site must attempt to contact the participant and reschedule the missed visit as soon as possible. Counsel the participant on the importance of maintaining the assigned visit schedule, and ascertain whether the participant wishes to and/or should continue in the study;
- Before a participant is deemed lost to follow-up, the investigator or designee must make every effort to regain contact with the participant (where possible, 3 telephone calls and, if necessary, a certified letter to the participant's last known mailing address or local equivalent methods). These contact attempts should be documented in the participant's medical record;
- Should the participant continue to be unreachable, the participant will be considered to have withdrawn from the study.

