5.3. Methods to Manage Missing Data

Any missing data were presented as part of a missing category except for those situations described as follows. For calculation of crude mortality, a participant with the last known survival status is before evaluation visit (i.e., Day 42, Day 84) or missing and the last assessment day is on or before the visit (i.e., Day 42, Day 84) will be treated as death. When change from baseline to a postbaseline value was calculated, only participants with baseline and at least one postbaseline value will be included in the calculation. In the time-to-event analysis, a participant without a reported death will be censored on the participant's last known alive day which will be the latest of randomization day, last study assessment day, latest study drug treatment day, date with follow-up therapies, date with AEs, last contact day, last PK sampling day, or date of discontinuation. For example, if a participant's last survival status is before day 42 and this participant's last known alive day is after Day 42, say day 50, then this participant will be censored on day 50.

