6.2. Secondary Endpoint(s)

6.2.1. Percentage of All-cause Mortality on Day 42 (Key Secondary Endpoint)

6.2.1.1. Main Analysis

- Estimand strategy: Treatment (Section 2.2.2).
- Analysis set: ITT population (Section 4). Any death that occurs after first dose of study drug through Day 42 will be included.
- Analysis methodology: The crude mortality rate will be summarized by number and percentage of participants through Day 42. The 2-sided 95% CIs for crude rate will be

calculated based on a binomial distribution. Any death that occurred after first dose of study drug through Day 42 will be included. A participant with the last known survival status is before Day 42 or missing and the last assessment day is before Day 42 will be treated as death.

- Intercurrent events and missing data: All data collected (after prohibited medication or after discontinuation of treatment) will be included. Missing data will be handled as described in Section 5.3.

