6.2.1.2. Sensitivity/Supplementary Analyses

A sensitivity analysis of all-cause mortality rate by Day 42 based on ITT population will be estimated using the KM method as described in Section 5.2.3.

Supplementary analyses of the same analysis described in Section 6.2.1.1 and KM method, respectively, will be repeated for mITT and myITT-IA populations.

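### The KM censoring rule accepts a discontinuation date without contact as a last-known-alive date, so participants lost to follow-up may stay at risk past the last evidence of life

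*SAP*

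**What the plan says.** SAP 5.3 sets the censoring rule for the KM curves: "a participant without a reported death will be censored on the participant's last known alive day which will be the latest of randomization day". The list goes on through assessment, dosing, follow-up therapy and adverse event dates and closes with "last contact day, last PK sampling day, or date of discontinuation". The SAP illustrates the rule with a participant whose last survival status precedes Day 42 but who is known alive later: "say day 50, then this participant will be censored on day 50".

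The rule feeds the analysis in SAP 6.2.1.2: "A sensitivity analysis of all-cause mortality rate by Day 42 based on ITT population will be estimated using the KM method". This is the only ITT analysis of the key secondary endpoint that the SAP calls a sensitivity analysis. The supplementary analyses repeat the crude and KM methods in other populations. SAP 6.2.2 carries the approach to Day 84, and SAP 6.3.1 uses KM to Day 180 for mucormycosis.

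The main analysis (SAP 6.2.1.1) treats missing status the opposite way. A participant whose last known survival status is before Day 42 or missing, and for whom "the last assessment day is before Day 42 will be treated as death", is counted as dead.

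Protocol 7.2 lists "Lost to follow-up" among the reasons for discontinuation from the study. Protocol 7.3 requires repeated attempts first ("where possible, 3 telephone calls and, if necessary, a certified letter to the participant's last known mailing address") and then states: "Should the participant continue to be unreachable, the participant will be considered to have withdrawn from the study".

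**The concern.** Every other item in the SAP 5.3 list from last assessment onward records something that happened to, or was learned about, the participant. The discontinuation date need not. In a latest-of rule it matters only when it falls after all the others. That happens in two quite different cases. In one, the participant withdrew in person or in writing, and the date is itself evidence of life. In the other, the site gave up on an unreachable participant, and it is not.

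In the second case, a participant last seen on Day 10 and recorded as lost on Day 50 is a death in the crude rate and an at-risk survivor through Day 42 in KM. KM is meant to show how much the crude result depends on counting missing status as death. Censoring at the last evidence of life would do that. The rule as written moves KM towards treating missing as survived, so the gap between the two analyses looks wider than it should.

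**Working it through.** **The plan's own figure.** The documents give no figure for the KM analysis or for loss to follow-up. The one design figure, in Protocol 9.5, is the 86.6% chance of seeing an adverse event of 3% incidence among 66 treated. It reproduces: 1 − 0.97^66 = 0.866. It supplies only N = 66 here. The step from 70 enrolled to 66 treated is attrition before dosing, not loss to follow-up.

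**Inputs.** Day 42 mortality of 19% is the isavuconazole ITT result of the earlier phase 3 aspergillosis trial (Protocol 2.2.4). The loss share, last-seen day, lag and timing of deaths are assumptions.

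**Check 1: constant hazard, loss declared after Day 42.** Let h = −ln(0.81)/42 = 0.00502 per day, L the loss share and t0 the last-seen day. Suppose the lost have the same hazard as the rest. Censoring at t0 then gives 19.0%. The SAP rule misses the deaths of the lost between t0 and Day 42, so KM mortality is lower by

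L × exp(−h·t0) × [1 − exp(−h·(42 − t0))].

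- L = 10%, t0 = 14: 0.10 × 0.932 × 0.131 = 1.22 points.
- L = 10%, t0 = 7: 0.10 × 0.965 × 0.161 = 1.55 points.
- L = 5%: half of these, 0.61 and 0.78 points.

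**Check 2: product-limit KM with 66 participants.** Take 13 observed deaths (0.19 × 66 = 12.5, rounded up) spread evenly over Days 2 to 41, with two by Day 7 and six by Day 21. Let m further participants have last contact on Day 7. Because nobody else is censored, the KM product collapses:

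- Censored at last contact: S(42) = 64/66 × (53 − m)/(64 − m).
- Discontinuation date 14 days later (Day 21): S(42) = 60/66 × (53 − m)/(60 − m).
- Discontinuation date after Day 42: S(42) = 53/66 for every m.

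Day 42 mortality, 1 − S(42):

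| Lost (m) | At last contact | 14-day lag | After Day 42 |
|---|---|---|---|
| 3 | 20.5% | 20.3% | 19.7% |
| 5 | 21.1% | 20.7% | 19.7% |
| 10 | 22.8% | 21.8% | 19.7% |

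Before rounding, the 14-day lag lowers mortality by 20.52 − 20.26 = 0.26 points for 3 lost and 22.78 − 21.82 = 0.96 points for 10 lost. Subtracting the one-decimal rates gives 0.2 and 1.0.

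With 5 lost and a date after Day 42, the 95% CI moves from 12.8–33.6% to 11.9–31.5%. The crude rule gives (13 + 5)/66 = 27.3% (exact CI 17.0–39.6%). The displayed gap is then 27.3 − 19.7 = 7.6 points, against 27.3 − 21.1 = 6.2 with censoring at last contact.

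**Day 84.** With 19 deaths assumed, 5 lost, last contact on Day 7 and a date after Day 84, KM mortality falls from 31.0% to 19/66 = 28.8%.

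**Check 3: lost participants with a different hazard.** Take L = 10% and t0 = 14.

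- Twice the hazard, declared lost after Day 42: true mortality is 20.06%, the SAP rule gives 17.78% and censoring at last contact gives 19.00%. Of the 2.28-point shortfall, the fix recovers 1.22. The other 1.06 is informative censoring.
- Half the hazard, declared lost on Day 28: true mortality and the SAP rule are both 18.41%, while censoring at last contact gives 19.00%.

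**The case against.** The strongest reply is that the governing term is the last known alive day, and that the Day 50 example describes someone actually known to be alive. Protocol 7.3 does not say which date is entered for a lost participant. SAP 5.3 does not say whether discontinuation means treatment or study. A treatment date would normally add little to the last dose date already listed. Data-entry instructions outside these documents may set the date to last contact. All of this stands, and it makes the point conditional: a reader might infer that the plan certainly carries lost participants as survivors, but the documents show only that the rule permits it.

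Three other stronger readings also fail.

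- A reader might infer that the bias is always downward. KM mortality under the SAP rule cannot exceed that from censoring at last contact, but against true mortality the direction depends on the hazard of the lost, as check 3 shows.
- A reader might charge the full 2.28 points of the doubled-hazard case to this phrase. Only 1.22 belongs to it.
- A reader might conclude that the discontinuation date should simply be deleted. Protocol 7.2.1 provides for written notice of withdrawal of consent, and such a date is valid evidence of life.

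It is also fair that a silence of 28 days or more is the long end. Protocol 7.3 wants missed visits chased promptly, and survival status is to be collected by telephone for those off treatment. Shorter lags shrink the effect.

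**Conclusion.** The point holds in conditional form. SAP 5.3 admits the discontinuation date as a last-known-alive date without requiring contact, and Protocol 7.3 describes how such a date can arise after the last evidence of life. If the later date is recorded, KM mortality is lower than with censoring at last contact.

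At 19% Day 42 mortality, with the lost at average hazard, last seen on Day 7 to 14 and declared lost after Day 42, the removable part is about 0.6 to 0.8 points at 5% loss and 1.2 to 1.6 at 10%. With last contact on Day 7 and a 14-day lag it is about 0.3 to 1.0 points for 3 to 10 of 66 lost. It is zero if the date is set to last contact, means treatment stop, or reflects withdrawal in person or in writing.

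These shifts are well inside the KM confidence interval. The endpoint is secondary and descriptive with no hypothesis test, and the main analysis already counts these participants as deaths. The priority is minor.

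**What to change.** In SAP 5.3, replace the last item of the list with: *date of discontinuation where contact with the participant or a representative confirmed the participant alive on that date; for participants lost to follow-up, censor at the last successful contact or other direct evidence of life*. If the sponsor already dates loss to follow-up to the last contact, one sentence saying so settles the matter.

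The cost is one SAP phrase and one derivation line, with no new data. Some participants are censored earlier, so KM intervals widen slightly. Bias from informative loss remains, because no choice of censoring date removes it.

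The list also names a randomization day in a study that randomises nobody. First dose day would be tidier, but as an early date in a latest-of list it should change no result.

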6. ANALYSES AND SUMMARIES

6.1. Primary Endpoint(s)

The primary endpoints are incidence rates of TEAEs by SOC and PT.

- Estimand strategy: Treatment (Section 2.2.1)
- Analysis set: Safety population (Section 4).
- Analysis methodology: the incidence rates will be calculated by dividing the number of participants with TEAEs by the number of participants in the safety population. All TEAEs will be coded using MedDRA and will be summarized (number and percentage) by SOC and PT. When a participant has the same AE reported multiple times during an analysis period based on preferred terminology (SOC, PT), the participant will be counted once at the preferred terminology level (Section 5.2.1).
- Intercurrent event and missing data: All data collected (after prohibited medication or after discontinuation of treatment) will be included.

6.2. Secondary Endpoint(s)

6.2.1. Percentage of All-cause Mortality on Day 42 (Key Secondary Endpoint)

6.2.1.1. Main Analysis

- Estimand strategy: Treatment (Section 2.2.2).
- Analysis set: ITT population (Section 4). Any death that occurs after first dose of study drug through Day 42 will be included.
- Analysis methodology: The crude mortality rate will be summarized by number and percentage of participants through Day 42. The 2-sided 95% CIs for crude rate will be

calculated based on a binomial distribution. Any death that occurred after first dose of study drug through Day 42 will be included. A participant with the last known survival status is before Day 42 or missing and the last assessment day is before Day 42 will be treated as death.

- Intercurrent events and missing data: All data collected (after prohibited medication or after discontinuation of treatment) will be included. Missing data will be handled as described in Section 5.3.

6.2.1.2. Sensitivity/Supplementary Analyses

A sensitivity analysis of all-cause mortality rate by Day 42 based on ITT population will be estimated using the KM method as described in Section 5.2.3.

Supplementary analyses of the same analysis described in Section 6.2.1.1 and KM method, respectively, will be repeated for mITT and myITT-IA populations.

6.2.1.3. Subgroup Analysis

If data permits, subgroup analyses of all-cause mortality on Day 42 will be performed based on the ITT population for the following subgroups:

- Age category 1: (≤ 45 , > 45 to ≤ 65 , > 65)
- Age category 2: (≤ 65 , > 65 to ≤ 75 , > 75)
- Gender (Male, Female)
- BMI category: (< 25 , ≥ 25 to < 30 , ≥ 30)
- eGFR category: < 60 , ≥ 60
- Baseline Neutropenic Status: Yes/No

6.2.2. Percentage of All-cause Mortality on Day 84

Percentage of all-cause mortality on Day 84 will be summarized and analyzed using the same approach as described in Sections 6.2.1.1-6.2.1.3.

6.2.3. The Crude Rate of Overall Response at EOT, Day 42, and Day 84

6.2.3.1. The Crude Rates of Overall Response at EOT

- Estimand strategy: While on-Treatment (Section 2.2.2).
- Analysis set: mITT and myITT-IA populations (Section 4).
- Analysis methodology: The crude rates of overall response based on investigator's assessment at EOT will be summarized by number and percentage of participants through

EOT. The 2-sided 95% CIs for crude rate will be calculated based on a binomial distribution.

- Intercurrent events and missing data: All data collected after use of the prohibited medications will be excluded. Missing data will be handled as described in Section 5.3.

6.2.3.1.1. Subgroup Analysis

If data permit, subgroup analyses will be performed for the overall response based on investigator's assessment at EOT based on mITT population for the aforementioned subgroups in Section 6.2.1.3, and the IFD location [lower respiratory tract disease (LRTD) only, LRTD plus Other Organ, Non LRTD only] .

6.2.3.2. The Crude Rates of Overall Response at Day 42 and Day 84

- Estimand strategy: While on-Treatment (Section 2.2.2).
- Analysis set: mITT and myITT-IA populations (Section 4).
- Analysis methodology: The crude rates of overall response based on investigator's assessment will be summarized by number and percentage of participants at Day 42 and Day 84, respectively. The 2-sided 95% CIs for crude rate will be calculated based on a binomial distribution.
- Intercurrent events and missing data: All data collected after use of the prohibited medications will be excluded. Missing data will be handled as described in Section 5.3. A participant that investigators' assessment indicated as Not Done at a visit will be considered as missing and will be included as a failure for the visit. Any death before Day 42 will be considered a failure by including in the death category for both timepoints. Any death occurring between Day 42 and Day 84 will be considered as a failure by including in the death category for Day 84.

6.2.4. Crude Success Rates of the Clinical, Mycological, Radiological Responses at EOT, Day 42 and Day 84

6.2.4.1. Clinical Response at EOT, Day 42 and Day 84

Outcome	Clinical response
Success	1. Resolution of all attributable clinical symptoms and physical findings 2. Resolution of some attributable clinical symptoms and physical findings
Failure	1. No resolution of any attributable clinical symptoms and physical findings and/or worsening 2. Results not available/Patient unevaluable
NA	No attributable signs and symptoms present at screening

- Estimand strategy: While on-Treatment (Section 2.2.2).

- Analysis set: mITT and myITT-IA populations (Section 4).
- Analysis methodology: Number and percent of participants in the categories of Success and Failure will be summarized at Day 42, Day 84 and EOT. The 2-sided 95% CIs for crude success rate will be calculated based on a binomial distribution.
- Intercurrent events and missing data: All data collected after use of the prohibited medications will be excluded. As the clinical response is one of the components toward the overall response, the results of clinical response will be summarized without regards to deaths. Missing data will be handled as described in Section 5.3. Any patient with a Not Done at a visit will be considered a missing and included as a failure. A participant with a NA assessment will be excluded from the denominators when calculating the percentages.

6.2.4.2. Mycological Response at EOT, Day 42 and Day 84

Outcome	Mycological assessment
Success	1. Eradication 2. Presumed Eradication
Failure	1. Persistence 2. Presumed Persistence
NA	1. No mycological evidence available at screening 2. No mycological follow-up results available

- Estimand strategy: While on-Treatment (Section 2.2.2).
- Analysis set: mITT and myITT-IA populations (Section 4).
- Analysis methodology: Number and percent of participants in the categories of Success and Failure will be summarized at Day 42, Day 84 and EOT. The 2-sided 95% CIs for crude success rate will be calculated based on a binomial distribution.
- Intercurrent events and missing data: All data collected after use of the prohibited medications will be excluded. As the mycological response is one of the components toward the overall response, the results of mycological response will be summarized without regards to deaths. Missing data will be handled as described in Section 5.3. A participant with a Not Done assessment at a visit will be considered missing and is included as a failure. A participant with a NA assessment will be excluded from the denominators when calculating the percentages.

6.2.4.3. Radiological Response at EOT, Day 42 and Day 84

Outcome	Radiological assessment
Success	1. $\geq 90\%$ improvement 2. $\geq 50\%$ to $< 90\%$ improvement 3. $\geq 25\%$ to $< 50\%$ improvement (for Day 42 only)
Failure	1. $< 25\%$ improvement at any time 2. Results not available
NA	No signs on radiological images at screening

An improvement between 25% and 50% from baseline is considered a radiological success for Day 42 and EOT (that is before Day 42). At least 50% improvement from baseline is considered a radiological success for visits on Day 42, Day 84 and EOT (that is after Day 42).

- Estimand strategy: While on-Treatment (Section 2.2.2).
- Analysis set: mITT and myITT-IA populations (Section 4).
- Analysis methodology: Number and percent of participants in the categories of Success and Failure will be summarized at Day 42, Day 84 and EOT. The 2-sided 95% CIs for crude success rate will be calculated based on a binomial distribution.
- Intercurrent events and missing data: All data collected after use of the prohibited medications will be excluded. As the radiological response is one of the components toward the overall response, the results of radiological response will be summarized without regards to deaths. Missing data will be handled as described in Section 5.3. A participant with a Not Done assessment at a visit will be considered missing and is included as a failure. A participant with a NA assessment will be excluded from the denominators when calculating the percentages.

6.2.5. Isavuconazole Plasma Concentrations at Day 3, 7, 14 and EOT Visit

- Analysis set: PK Concentration population (Section 4).
- Analysis methodology: Observed plasma concentrations of isavuconazole will be summarized for Day 3, Day 7, Day 14, and EOT using descriptive statistics.

6.3. Exploratory Endpoints**6.3.1. Percentage of All-cause Mortality on Day 42 and Day 84 in Participants with IM**

The endpoints will be analyzed using the same method from the key secondary endpoint (Section 6.2.1.1) for myITT-IM population (Section 4). As a supplementary analysis, all-cause mortality rate over time by Day 42, Day 84, Day 120, and Day 180 based on myITT-IM population will also be estimated using the KM method as described in Section 5.2.3. This analysis will generate a survival curve from Day 1 through Day 180.

6.3.2. The Crude Rate of Overall Response at EOT, Day 42, and Day 84 in Participants with IM.

The endpoints will be analyzed using the same method from the secondary endpoints in Section 6.2.3) for myITT-IM population (Section 4).

6.3.3. Crude Success Rate of the Clinical, Mycological, Radiological Responses at EOT, Day 42, and Day 84 in Participants with IM.

The endpoints will be analyzed using the same method from the secondary endpoints in Section 6.2.4 for myITT-IM population (Section 4).

CCI

